### **3.6.5. EVALUATION OF PHARMACOKINETIC PARAMETERS**

The procedures for obtaining ALX-0061 serum concentrations are found in section [3.4.3](#).

#### **Evaluation of Pharmacokinetics**

PK analysis will be performed on the PK population.

Individual study drug concentrations will be listed. In addition a listing of the actual sampling times relative to the study drug administration times will be presented.

Drug concentrations will be summarized by treatment group and scheduled sampling time.

The descriptive statistics on drug concentrations will be performed under the responsibility of Ablynx NV.

#### **Pharmacokinetic Model**

ALX-0061 serum concentrations obtained from all subjects in the study will be pooled together with available data collected so far in previous studies. A population PK analysis will be conducted to describe the population mean and variability of ALX-0061 exposure in the study population based on pharmacostatistical nonlinear mixed effect models.

PK Modelling will be performed under the responsibility of Ablynx NV. Results will be provided in a separate Modelling and Simulation report.

### 3.6.6. EVALUATION OF PHARMACODYNAMIC PARAMETERS

All PD data will be summarized using descriptive statistics and will be listed and summarized in tabular and/or graphical form. Additional exploratory modelling (e.g., predictive analysis of specific biomarkers) may be performed.

#### Exposure-response Model(s)

An Exposure-Response analysis will be performed to determine the relationship between ALX-0061 serum exposure and PD and efficacy endpoints i.e., DAS28 and ACR20 using nonlinear mixed effects modelling.

Details on the exposure-response modelling will be included in a separate Data Analysis Plan, and will be performed under the responsibility of Ablynx NV. Results of this analysis will be provided in a separate Modelling and Simulation report.

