**Immunogenicity:**

- Determination of anti-ALX-0061 antibodies (ADA) and potentially further characterization by modified ADA assay (mADA) and neutralizing antibody assay (nAb).

**Statistical Methods:***Sample Size and Power*

Up to approximately 330 subjects in 5 treatment arms randomized in a 1:1:1:1:1 ratio.

Simulations were performed to evaluate the power for detecting a significant trend effect in the different ALX-0061 doses versus placebo. Assuming Week 12 ACR20 response rates of 25%, 30%, 45%, 55%, and 55% for placebo, ALX-0061 75 mg q4w, ALX-0061 150 mg q4w, ALX-0061 150 mg q2w, and ALX-0061 225 mg q2w respectively, a sample size of 66 subjects per arm will provide more than 90% power using the Cochran Armitage test for trend at significance level of 0.05 (2-sided).

*Primary Efficacy Endpoint Evaluation:*

For the descriptive statistics and trend test on the primary efficacy endpoint (primary efficacy analysis), data will be analyzed according to the intent-to-treat principle; thus, subjects will be analyzed according to the treatment for which they were assigned. Subjects with missing ACR20 response at Week 12 will be treated as non-responders (non-responder imputation approach).

Additionally, exploratory comparisons of each separate dose versus placebo will be conducted using a Chi or Fisher exact test (or other test if deemed more relevant). The study is only powered for testing the trend of the primary endpoint. All other p-values are exploratory and no correction for multiple testing is foreseen.

---

Primary efficacy endpoint evaluation will also be performed using the per-protocol population as a sensitivity analysis.

*All Other Evaluations:*

For continuous secondary efficacy endpoints (including DAS28, CDAI, SDAI), summary statistics, such as mean with standard deviation and median and associated 95% confidence intervals will be determined. For categorical efficacy endpoints the point estimate together with the 95% confidence interval will be calculated. Summary statistics will be provided by treatment group.

All safety, PD and immunogenicity analyses will be performed using the safety population of all subjects who received at least 1 dose of study drug. Analyses will be performed using the treatment that the subject actually received.

All these data will be summarized using descriptive statistics as appropriate.

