PK/PD modelling will be performed to characterize the relationship between ALX-0061 exposure and the efficacy endpoints. The results of this exploratory analysis will be presented in a separate report.

---

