## 2. OBJECTIVES

Primary objective:

- To assess the efficacy and safety of dose regimens of ALX-0061 administered s.c. in combination with MTX to subjects with active RA despite MTX therapy compared with placebo.

Secondary objective:

- To assess the effects of ALX-0061 on quality of life, PK, PD, and immunogenicity of ALX-0061, and to define the optimal dose regimen for ALX-0061, based on safety and efficacy, for further clinical development.

[figure not shown]

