### 3.6.7. EVALUATION OF SAFETY PARAMETERS

The DSMB will evaluate the safety data periodically (see section [3.4.5](#)).

The following analyses will be performed to assess the safety of subjects in this study.

- The incidence and type of AEs.
- The incidence and type of SAEs.
- The incidence and type of related AEs (including study drug injection-site reactions and hypersensitivity reactions).
- The laboratory parameters and change from baseline in these laboratory parameters.
- The incidence of antibodies to ALX-0061.

All safety, PD and immunogenicity analyses will be performed using the Safety Population of all subjects who received at least 1 dose of study drug. Analyses will be performed using the treatment that the subject actually received.

In addition, subgroup analyses will be performed to evaluate consistency of safety over covariates including demographics (including weight), and concomitant medication (including immunosuppressants and corticosteroids).

AEs will be fully described and coded according to the Medical Dictionary for regulatory Activities. A treatment-emergent analysis of AEs will be done. Frequency of subjects presenting AEs, AEs leading to withdrawal, adverse drug reactions, and

---

SAEs will be tabulated for each treatment group by system organ class and preferred term.

For laboratory parameters, descriptive statistics (mean, median, standard deviation, minimum, and maximum) will be computed on the actual values and the change from baseline (absolute) for each parameter. All laboratory values will be categorized according to their normal ranges as below, within or above normal. A shift table versus baseline (including final value versus baseline and worst value versus baseline) will be created.

Vital signs variables will be fully depicted using descriptive statistics (for actual values and changes from baseline) and shift tables according to their normal ranges. Screening ECG values will be assessed through listing of individual results by subject and summary tables.

Abnormal findings in physical examinations will be listed.

Immunogenicity will be assessed through listing of individual results by subject and summary tables.

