### **3.6.8. DETERMINATION OF SAMPLE SIZE**

Simulations were performed to evaluate the power for detecting a significant trend effect in the different ALX-0061 doses versus placebo. Assuming ACR20 response rates of 25%, 30%, 45%, 55%, and 55% for placebo, ALX-0061 75 mg q4w, ALX-0061 150 mg q4w, ALX-0061 150 mg q2w, and ALX-0061 225 mg q2w respectively, a sample size of 66 subjects per arm will provide more than 90% power using the Cochran Armitage test for trend at significance level of 0.05 (2-sided).

Drop-out rate is assumed to be low (i.e., between 5 and 15%) and considered equally distributed between subjects receiving placebo and ALX-0061. Subjects who drop-out are considered as non-responders (non-responder imputation approach).

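### The regimen is to be chosen on safety as well as efficacy, but no planned analysis relates exposure or dose to safety or estimates a safety difference between regimens

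*Combined protocol and SAP*

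**What the plan says.** Section 2 of the protocol puts safety into both objectives. The primary one is "To assess the efficacy and safety of dose regimens of ALX-0061 administered s.c. in combination with MTX", against placebo. The secondary one is "to define the optimal dose regimen for ALX-0061, based on safety and efficacy, for further clinical development".

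Efficacy gets several inferential tools. Section 3.6.4 plans 95% confidence intervals for the group summaries. Section 3.6.4.1 plans a trend test on Week 12 ACR20 and exploratory tests of each dose against placebo. Section 3.6.6, under Exposure-response Model(s), plans nonlinear mixed-effects modelling of "the relationship between ALX-0061 serum exposure and PD and efficacy endpoints i.e., DAS28 and ACR20". The synopsis is narrower still: the modelling is to "characterize the relationship between ALX-0061 exposure and the efficacy endpoints". Section 3.6.6 adds: "Details on the exposure-response modelling will be included in a separate Data Analysis Plan".

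Safety gets summaries. Section 3.6.7 plans adverse-event frequencies by treatment group, shift tables, listings and subgroup summaries. For laboratory variables, "descriptive statistics (mean, median, standard deviation, minimum, and maximum) will be computed on the actual values and the change from baseline". The synopsis says of the safety, PD and immunogenicity data: "All these data will be summarized using descriptive statistics as appropriate".

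Section 3.6.8 fixes the planning rates: "Assuming ACR20 response rates of 25%, 30%, 45%, 55%, and 55% for placebo", 75 mg q4w, 150 mg q4w, 150 mg q2w and 225 mg q2w in that order.

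**The concern.** An objective that selects a regimen on two criteria needs an analysis that informs the choice on both. Here efficacy is carried to a modelled exposure-response curve, while safety stops at tables by arm. The plan specifies no between-regimen safety difference, no interval for one, no dose trend and no exposure-safety relation.

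The gap bites hardest at the top of the dose range. If the two q2w regimens have the same Week 12 ACR20 rate, that endpoint cannot choose between them and safety carries more of the decision. Anyone comparing the safety tables by eye would be comparing 66 subjects with 66, with no stated precision. A real gradient could be overlooked, or a chance difference over-read. Safety contrasts chosen after the Week 24 data are seen would also be open to the charge of selection.

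The protocol gives product-specific reasons to look. Section 1.2.4.2 reports injection-site reactions that seemed to rise with dose over 50 to 300 mg, all mild and transient. Section 1.2.5 reports reversible falls in neutrophils and platelets in most subjects of the Phase I/II study.

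**Working it through.** **1. The plan's own figure.** Inputs (section 3.6.8): rates 25/30/45/55/55%, 66 per arm, Cochran-Armitage test, two-sided 0.05. Simulation with 200,000 trials gives 99.5% power with equally spaced scores and 99.1% with scores of 0/75/150/300/450 mg per 4 weeks. The stated figure of more than 90% is correct and conservative. It concerns the ACR20 trend and says nothing about safety or about the top two arms.

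**2. What ACR20 says about the top two arms.** At 55% in each, the 95% half-width of their difference is

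1.96 × √(2 × 0.55 × 0.45 / 66) = 0.170, or about 17 points.

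**3. What safety tables of 66 against 66 can show.** The documents give no safety rates, so the rates below are assumptions.

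SE = √[(p₁(1−p₁) + p₂(1−p₂))/66]; half-width = 1.96 × SE; power ≈ Φ(|p₂−p₁|/SE − 1.96). Using the pooled variance under the null gives the lower power in each pair.

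| Assumed rates | SE | Half-width | Power | Fisher exact power | n per arm for 80% |
|---|---|---|---|---|---|
| 5% v 10% | – | 8.9 points | 19% | 10% | 435 |
| 5% v 15% | √(0.175/66) = 0.0515 | 10.1 points | 48-49% | 37% | 141 |
| 10% v 20% | √(0.250/66) = 0.0615 | 12.1 points | 36-37% | 28% | 199 |
| 15% v 30% | – | 14.0 points | 54% | 47% | 121 |

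For 10% v 20%: 0.10/0.0615 − 1.96 = −0.335, and Φ(−0.335) = 0.369.

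For rare events: at a true rate of 1%, the chance of seeing none in 66 subjects is 0.99⁶⁶ = 0.515.

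For a continuous laboratory variable, the difference detectable with 80% power is (1.96 + 0.842) × √(2/66) = 0.49 SD. Laboratory means are thus more informative than event counts, but no comparison is planned for them either.

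**4. Are the inputs for a better analysis already there?** Section 3.6.5 plans a population PK model using concentrations from all subjects, which supplies individual exposure estimates. Blood counts, liver enzymes, lipids and adverse events are all collected under section 3.4.5. Only the link between the two is missing.

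**The case against.** Several counter-arguments have force.

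*Descriptive safety analysis is usual in Phase IIb, and the detail may sit elsewhere.* Section 3.6.2 leaves detail to an SAP finalised before the Week 24 lock, and section 3.6.6 leaves the modelling detail to a separate Data Analysis Plan, which is not among the documents. Either could add safety. But the protocol states the scope of the model and closes it at DAS28 and ACR20, so nothing commits the sponsor to safety. Section 3.6.6 also allows optional further modelling, but its example is biomarkers. The DSMB's stated function is subject safety, not regimen choice.

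*Pairwise differences can be computed from the tables.* True, and they will be imprecise either way. Naming them in advance settles which contrasts are reported.

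A reader might also infer more than the documents support:

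- *That safety alone must decide between the q2w regimens.* The 55%/55% pair is a planning assumption for Week 12 ACR20. Section 3.1.1 also relies on ACR50/70, remission and early time points, and chose the regimens from modelled DAS28 response. These may separate the arms.
- *That a rise in liver enzymes or lipids is expected with this drug.* Section 1.2.5 reports such rises for IL-6 inhibition in general. For ALX-0061 it reports no clinically relevant trend in mean liver or lipid parameters in either study, individual subjects aside. Apart from injection-site reactions, section 1.2.4.2 reports no dose-related adverse event. No dose relation is stated for the neutrophil and platelet falls.
- *That a five-arm trend would resolve the top two regimens.* If rates rise linearly with 4-weekly dose from 5% to 15%, the trend test has about 61% power, but the top two arms are then 11.7% and 15% and their pairwise power is only 8-9%. With a plateau (5, 6.7, 10, 15, 15%) trend power is about 65% although the top two do not differ. A significant trend therefore says nothing specific about that pair.
- *That a straight line in dose makes the top-two difference much more precise.* The standard error would fall from √(2/66) = 0.174 SD to 150/√(66 × 130,500) = 0.051 SD, but only by assuming linearity. Section 1.2.4.1 reports exposure rising more than proportionally with dose, and the planning rates plateau. A line fitted to those rates has slope 93/130,500 per mg, so it gives 150 × 93/130,500 = 0.107, or 10.7 points, between 150 mg q2w and 225 mg q2w, where the plan assumes none.

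**Conclusion.** The point holds as a mismatch between objective and analysis. The protocol sets out to choose a regimen on safety and efficacy, models exposure against PD and efficacy only, and plans no estimate that relates dose or exposure to safety or compares regimens on it.

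The precision figures (half-widths of about 10 to 12 points and power of about 36% to 49% for 10-point differences) rest on assumed event rates, 66 subjects per arm with no loss, and normal approximations; exact tests do slightly worse. They show how little the tables by arm can say about two regimens. They do not show that a safety difference exists, nor that modelling would settle the matter: any gain depends on the shape assumed, and rare events stay out of reach.

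This is an inexpensive improvement to the analysis. It does not threaten the primary analysis, whose stated power is confirmed.

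**What to change.** **Section 3.6.6 and the Data Analysis Plan.** Extend the exposure-response analysis to named safety variables already collected. Take neutrophil count, platelet count and injection-site reactions first, since the protocol reports effects of ALX-0061 on these. Then add ALT/AST, lipids and infections, noting that section 1.2.5 found no clinically relevant mean liver or lipid trend. Use the same individual exposure estimates as for efficacy, and a model form that allows a plateau instead of imposing linearity in dose. Align the synopsis.

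**Section 3.6.7.** For the same variables, report the 225 mg q2w minus 150 mg q2w and the 150 mg q2w minus 150 mg q4w differences with 95% confidence intervals, labelled exploratory. These keep a randomised comparison beside the model, which relies on exposure that is not randomised.

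Fix both before the Week 24 database lock.

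**Cost.** Wording in the plan and some modelling time. No new patients, visits or samples, and no change to clinical rules. The downside is more exploratory estimates to interpret, without multiplicity control, which stay imprecise for rare events.

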### 3.6.7. EVALUATION OF SAFETY PARAMETERS

The DSMB will evaluate the safety data periodically (see section [3.4.5](#)).

The following analyses will be performed to assess the safety of subjects in this study.

- The incidence and type of AEs.
- The incidence and type of SAEs.
- The incidence and type of related AEs (including study drug injection-site reactions and hypersensitivity reactions).
- The laboratory parameters and change from baseline in these laboratory parameters.
- The incidence of antibodies to ALX-0061.

All safety, PD and immunogenicity analyses will be performed using the Safety Population of all subjects who received at least 1 dose of study drug. Analyses will be performed using the treatment that the subject actually received.

In addition, subgroup analyses will be performed to evaluate consistency of safety over covariates including demographics (including weight), and concomitant medication (including immunosuppressants and corticosteroids).

AEs will be fully described and coded according to the Medical Dictionary for regulatory Activities. A treatment-emergent analysis of AEs will be done. Frequency of subjects presenting AEs, AEs leading to withdrawal, adverse drug reactions, and

---

SAEs will be tabulated for each treatment group by system organ class and preferred term.

For laboratory parameters, descriptive statistics (mean, median, standard deviation, minimum, and maximum) will be computed on the actual values and the change from baseline (absolute) for each parameter. All laboratory values will be categorized according to their normal ranges as below, within or above normal. A shift table versus baseline (including final value versus baseline and worst value versus baseline) will be created.

Vital signs variables will be fully depicted using descriptive statistics (for actual values and changes from baseline) and shift tables according to their normal ranges. Screening ECG values will be assessed through listing of individual results by subject and summary tables.

Abnormal findings in physical examinations will be listed.

Immunogenicity will be assessed through listing of individual results by subject and summary tables.

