  - In study ALX0061-C102, results indicate a trend towards a minor decrease in fibrinogen and (hs)CRP levels following administration of ALX-0061 in most subjects.
- Suppression of IL-6 signaling has been shown to lead to decreases in neutrophil and platelet counts [\[19\]](#).
  - In study ALX-0061-1.1/10, a rapid and reversible decrease in neutrophils and platelets was seen in the majority of subjects after administration of ALX-0061. No TEAEs related to the decreases in neutrophil and platelet count (or other hematology parameters) were reported, except for 1 subject with mild leukopenia (without neutropenia; MAD part of the study).
  - In study ALX0061-C102, the results show a tendency towards a transient and mild decrease neutrophil count.

- Increased transaminase levels (AST/ALT) in serum and increased cholesterol (HDL, LDL and triglycerides) levels have been reported following pharmacological inhibition of the IL-6 pathway [20]. With the exception of individual subjects showing increases beyond the normal range, there were no clinically relevant trends in mean liver (ALT/AST/GGT/LDH/bilirubin) parameters, mean lipid concentrations, or other safety-related biochemistry parameters across dose levels in study ALX-0061-1.1/10 or ALX0061-C102.
- Recent data indicate that RA subjects have a generally increased rate of gastrointestinal (GI) perforation [21]. At this time, it is not clear whether IL-6 inhibitors further increase the risk of this complication beyond that observed in the general RA population. To date, no cases of GI perforation have been observed following ALX-0061 administration.
- As with all therapeutic proteins used in humans, infusion reactions (e.g., either anaphylactic or anaphylactoid) cannot be excluded.
  - In study ALX-0061-1.1/10, two hypersensitivity reactions were reported (one serious and one moderate). For additional details, please refer to the Investigator's Brochure.
  - In study ALX0061-C102, no hypersensitivity reactions were reported.
- Administration of any protein therapeutic can lead to the development of ADA [22]. The currently available immunogenicity (ADA) results after i.v. and s.c. administration of ALX-0061 do not indicate meaningful risks related to pre-existing or treatment-emergent antibodies to ALX-0061.

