12. Have received intra-articular (i.a.), intramuscular (i.m.), or i.v. corticosteroids during the 4 weeks prior to screening.

13. Have received approved or investigational biological or targeted synthetic DMARD therapies for RA (including TNF  $\alpha$  inhibitors, abatacept, rituximab, or Janus kinase [JAK]-inhibitors) less than 6 months prior to screening. For subjects who received prior rituximab, subjects with an inadequate recovery of B cells should be excluded regardless of when they received rituximab.
14. Have a history of toxicity, non-tolerance, primary non-response or inadequate response to a biological therapy, or targeted synthetic DMARDs (including JAK inhibitors), for RA.
15. Have received prior therapy blocking the IL-6 pathway, such as but not limited to ALX-0061, sirukumab, sarilumab, clazakizumab, olokizumab, tocilizumab (TCZ) at any time, will be excluded.
16. Have a known hypersensitivity to the active product or any excipient of the study drug.
17. Abnormality in screening laboratory test results:
  - a. ALT and/or AST levels  $\geq$  1.5 times the ULN.
  - b. Hemoglobin levels  $\leq$  85 g/L (8.5 g/dL).
  - c. Platelet count  $\leq$   $125 \times 10^9/L$  (125,000 cells/mm $^3$ ).
  - d. White blood cell count  $\leq$   $3.5 \times 10^9/L$  (3,500 cells/ mm $^3$ ); neutrophils:  $\leq 2 \times 10^9/L$ .
  - e. Serum creatinine levels  $\geq$  1.5 mg/dL (133  $\mu$ mol/L).
  - f. Any other clinically significant abnormal screening laboratory results as evaluated by the Investigator.
18. Positive screening for hepatitis B, hepatitis C, or HIV.
19. At the discretion of the treating physician, subjects with impaired cellular or humoral immunodeficient (i.e., Ig deficiency, IgA, IgG etc.) disorders should be excluded.
20. History or presence of alcohol or drug abuse.
21. Blood donation ( $> 500$  mL) or a blood loss of comparable volume within 3 months prior to first dosing.
22. Planned donation of germ cells, blood, organs, bone marrow during the course of the study or within 6 months thereafter.
23. Male with female partner who is planning to become pregnant within 6 months of last dosing.
24. Pregnant women or female subjects who are breastfeeding.
25. History of anaphylactic reaction.
26. Administration of a live, attenuated vaccine within 3 months before dosing with ALX-0061, or anticipation that such a live attenuated vaccine will be required during the study or within 6 months after last dosing.

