##### **Study drug must also be permanently discontinued if any of the following occurs:**

- Serious hypersensitivity reaction.
- Following abnormalities in laboratory test results: ALT and/or AST elevations between > 3 and  $\leq$  5 x ULN (confirmed by repeat testing on 2 consecutive visits),

ALT or AST elevations  $> 5 \times$  ULN, absolute neutrophil count  $< 1 \times 10^9/L$ , or a platelet count  $< 50 \times 10^3/\mu L$ .

- Diagnosis of or suspicion of a serious infection (requiring parenteral antibiotic and/or hospitalization) or TB.
- Malignancy.
- Pregnancy or pregnancy planned within the study period.
- Demyelinating disease.
- The initiation of protocol-prohibited medications (see section [3.3.6](#)).
- Congestive heart failure (CHF) class III or IV as defined by the New York Heart Association, unstable angina pectoris, myocardial infarction, cerebrovascular accident.
- In case of interruption of study drug administration for 2 consecutive doses.
- The randomization code is broken prematurely by the Investigator or his/her staff.
- The Investigator or the Sponsor's medical monitor deems it is in the subject's best interest.

Discontinuation of study drug must be considered for subjects who develop a severe study drug injection-site reaction or a severe hypersensitivity reaction.

Subjects who have to discontinue according to these criteria but are not withdrawing consent for post-treatment follow-up should return for the Early Termination Visit planned 2 weeks after the last study drug administration (unless they discontinue during a study visit, in which case that becomes their Early Termination Visit). Subjects should also have a Follow-up Visit planned 12 weeks after the last study drug administration, according to section [3.4.1.3](#).

A description of assessments to be performed for subjects who discontinue from the study is provided in section [3.4.1.3](#) (also see Early Termination Visit in the [Schedule of Assessments](#)).

For all subjects, every effort should be made to contact the medical monitor prior to discontinuing study drug, where medically feasible. If there is a medical reason for discontinuation, the subject will remain under the supervision of the Investigator until satisfactory health has returned unless the subject withdraws his consent and is no longer willing to come to the visits. Subjects who discontinue will not be replaced.

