### **3.5.1.1. AE SEVERITY**

The severity of AEs will be rated on a 3-point scale according to the Common Terminology Criteria for AEs (CTCAE v4.0):

- Mild: discomfort noticed but no disruption of normal daily activity (signified by grade 1 of CTCAE v4.0).
- Moderate: discomfort sufficient to reduce or affect normal daily activity (signified by grade 2 of CTCAE v4.0).
- Severe: incapacitating with inability to work or perform normal daily activity, (signified by grade 3 or 4 or 5 of CTCAE v4.0).

It is emphasized that the term severe is a measure of intensity: a severe AE is not necessarily serious.

Please refer to the Common Terminology Criteria for Adverse Events (CTCAE v4.0) for assessment of severity of AEs related to laboratory abnormalities.

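### The three-class laboratory shift tables in section 3.6.7 cannot separate mild from stopping-level ALT/AST rises, and show no shift at all for subjects who enter already above normal

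*Combined protocol and SAP*

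**What the plan says.** Section 3.6.7 gives one rule for classifying laboratory results: "All laboratory values will be categorized according to their normal ranges as below, within or above normal". It then states: "A shift table versus baseline (including final value versus baseline and worst value versus baseline) will be created". The only other laboratory summary there is the mean, median, standard deviation, minimum and maximum of each parameter and of its change from baseline. The section names no toxicity grade, no band in multiples of the ULN and no count of subjects reaching a given limit.

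Three other parts of the protocol bear on this:

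- **Entry (section 3.2.2, criterion 17).** Subjects are excluded if their "ALT and/or AST levels" are at or above "1.5 times the ULN", if platelets are at or below 125 x 10^9/L, or if neutrophils are at or below 2 x 10^9/L, all at screening.
- **Mandatory stopping (section 3.2.3.2).** The item that opens "Following abnormalities in laboratory test results: ALT and/or AST elevations between" requires permanent discontinuation of study drug for ALT/AST above 3 and up to 5 times the ULN if confirmed on two consecutive visits, ALT or AST above 5 times the ULN, neutrophils below 1 x 10^9/L, or platelets below 50 x 10^3/µL.
- **Grading (section 3.5.1.1).** CTCAE v4.0 is invoked "for assessment of severity of AEs related to laboratory abnormalities", so it applies to adverse events as rated by the investigator. It is not applied to the laboratory data.

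**The concern.** These are risks that the protocol itself names. Section 1.2.5 says "Suppression of IL-6 signaling has been shown to lead to decreases in neutrophil and platelet counts", and in the same list it cites raised transaminases under IL-6 pathway inhibition. Safety is part of the primary objective, and the secondary objective includes choosing the best regimen on safety and efficacy together (section 2). For four active regimens, a useful laboratory comparison is how many subjects in each arm reached a level that matters.

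The planned categorical table does not provide that. Its classes change only at the edge of the normal range, while the protocol's own decisions are taken well outside it. Subjects may also enter already beyond that edge for ALT/AST, and for them the table has nowhere further to move.

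**Working it through.** The plan states no figure to reproduce here. The check applies the section 3.6.7 rule to values that the entry and stopping limits allow.

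**Rule.** A value is *below* if under the lower limit of normal (LLN), *above* if over the ULN, and otherwise *within*. The shift compares the baseline class with the class of the worst value.

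**ALT/AST, in multiples of the ULN.** Entry and stopping limits are both stated in this unit, so no assumed normal range is needed.

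| Baseline | Worst value | Shift recorded |
|---|---|---|
| 0.8 | 1.6 | within to above |
| 0.8 | 10 | within to above |
| 1.2 | 1.6 | above to above |
| 1.2 | 5.5 | above to above |
| 1.49 | 10 | above to above |

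Two results follow. Any baseline above 1.0 and below 1.5 gives no shift, whatever level is reached; baselines of 1.01, 1.2 and 1.49 were tried against worst values of 1.6, 3.5, 5.5 and 10. From a normal baseline, a rise to 1.6 and a rise to 10 land in the same cell, although only the second is past the stop at 5.

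**Neutrophils, x 10^9/L.** The documents give no LLN, so it was varied from 1.5 to 2.5 as an assumption. At every value tried (1.5, 1.8, 2.0, 2.1, 2.5), worst values of 1.4 and 0.9 are both *below*, although only 0.9 is under the stop at 1. In general, the *below* class mixes mild and stopping-level values whenever the LLN is above 1.

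**Platelets, x 10^9/L** (the same unit as 10^3/µL). The LLN is again an assumption, varied from 120 to 160. The case is a fall to 45, under the stop at 50.

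| Assumed LLN | Baseline 126 | Baseline 135 | Baseline 145 |
|---|---|---|---|
| 120 or 125 | within to below | within to below | within to below |
| 130 | no shift | within to below | within to below |
| 140 | no shift | no shift | within to below |
| 150 or 160 | no shift | no shift | no shift |

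The no-shift case therefore exists only if the LLN is above 125. At or below 125, nobody can pass screening with a platelet count already below normal.

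**With the protocol's own limits as cut points.** Take ALT/AST bands of up to 1, above 1 to 3, above 3 to 5, and above 5. A baseline of 1.2 with a worst value of 5.5 moves from the second band to the fourth. Splitting neutrophils at 1 separates 1.4 from 0.9. Splitting platelets at 50 makes a fall from 135 to 45 change class.

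**The case against.** The strongest reply is that the shift table is not the whole safety analysis. A reader might infer that stopping-level results disappear, or that laboratory changes reach the adverse event data only when an investigator calls them clinically significant. The documents support neither reading. Section 3.4.5.2 does require clinically significant findings to be recorded, but section 3.4.5.1 lists further routes, including any result that would require a dosing change or discontinuation. A result at a section 3.2.3.2 limit is therefore reportable by rule. Section 3.5.1.4 records withdrawal of drug as the action taken, and section 3.6.7 tabulates events that led to withdrawal by arm. Group minima and maxima would also show that an extreme value occurred, and a DSMB reviews safety data periodically.

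That stands, and it narrows the point without closing it:

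- The adverse event route depends on investigator reporting and preferred-term coding. Section 3.6.7 names no table by severity.
- A single unconfirmed ALT/AST value above 3 and up to 5 times the ULN does not trigger the stop, so the discontinuation route does not by itself capture it.
- A minimum or maximum does not say how many subjects were affected.
- Section 1.2.5 shows how the sources can diverge. In the earlier RA study most subjects had falls in neutrophils and platelets, yet the only related event was one mild leukopenia. Individual liver values rose beyond normal without a clinically relevant trend in the means.

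A second reply is that section 3.6.2 leaves detail to a SAP, which could add grading. No separate SAP text is in the document reviewed, so the point can be made only of the protocol's section 3.6.7.

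**Conclusion.** The point holds for the laboratory shift tables described in section 3.6.7. For ALT/AST it follows from the entry and stopping limits alone. For neutrophils it needs an LLN above 1 x 10^9/L, and for the platelet no-shift case an LLN above 125 x 10^9/L; both are assumptions.

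The number of subjects affected cannot be estimated. The documents give neither the share entering with raised ALT/AST nor the expected frequency of stopping-level values. What is certain is that section 3.6.7 plans no per-arm count of subjects by threshold for the laboratory risks that the protocol names. This is a gap in reporting that should be closed. It does not show that subjects at a stopping limit would go unnoticed during the trial.

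**What to change.** In section 3.6.7 and in the SAP, which section 3.6.2 says is finalized before the Week 24 database lock, keep the normal-range shift tables and add:

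1. Per-arm counts and percentages of subjects whose worst post-baseline value crosses each laboratory limit already in section 3.2.3.2: ALT/AST above 3 and above 5 times the ULN, neutrophils below 1 x 10^9/L, and platelets below 50 x 10^3/µL. State that the above-3 count uses the single worst value, so it is wider than the confirmed-on-two-visits stopping rule.
2. Shift tables from baseline to worst post-baseline CTCAE v4.0 grade for neutrophils, platelets, ALT and AST, using the scale that section 3.5.1.1 already adopts.

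A count of raised ALT or AST with concurrent raised bilirubin, and grading of other parameters, are optional.

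The cost is a few extra tables from central laboratory data already collected. No new samples or visits are needed, and no clinical rule changes.
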